2. To assess adverse events following cholecystectomy (e.g., bile duct injury) and their management.
3. To analyse rates and outcomes of unsuspected gallbladder cancer.
4. To evaluate the global variation in the availability of cholecystectomy services and training amongst included hospitals.
5. To assess sustainable practices in laparoscopic cholecystectomy globally.

AUDIT STANDARDS

Pre-operative

1. **Interventional radiology service:** There should be 24-hour access to interventional radiology to support the delivery of an emergency HPB service [11].
2. **Risk Stratification:** For patients with acute cholecystitis, surgeons may use the Tokyo Guidelines 18 (TG18) [8].
3. **Timing of surgery:** In patients presenting with acute cholecystitis, the optimal timing for cholecystectomy is within 48 hours, and no more than 10 days from symptom appearance [7].

Intra-operative

1. **Critical Safety View (CVS):** The use of the CVS during laparoscopic cholecystectomy (achieving all 3 components – Figure 1) is the recommended approach to correctly identify relevant anatomy and minimize the risk of bile duct injuries [7,8]:
 - I. **Clearance of the hepatocystic triangle:** The HC triangle should be cleared of all the fibro-fatty and soft areolar tissue.
 - II. **Exposure of the lower cystic plate:** The gallbladder should be separated from its liver bed to expose at least the lower third of the cystic plate.
 - III. **Only two tubular structures should be seen entering the gallbladder:** the cystic duct and the cystic artery.

[figure not shown]

Figure 1: Photographs showing the critical view of safety.

2. **Intraoperative imaging:** in patients with uncertainty of biliary anatomy or suspicion of bile duct injury, intraoperative imaging (e.g. cholangiogram, laparoscopic ultrasound and incisionless cholangiography with fluorescence) may help delineate relevant anatomy, detect bile duct stones, and decrease the risk of bile duct injury [7,8,12].
3. **Bailout Procedures:** When CVS cannot be achieved and the biliary anatomy cannot be clearly defined by other methods (e.g. imaging) during laparoscopic cholecystectomy, surgeons should

consider a bailout procedure (e.g. subtotal cholecystectomy or total cholecystectomy by the fundus-first (top down) approach) [7].

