GlobalSurg (<http://globalsurg.org/>) is a collaboration between practising surgeons from around the world, performing research in surgery to foster local, national and international research networks. The collaborative model used has previously been described elsewhere [13] and has already facilitated three multicentre, international, prospective cohort studies including a total of 46,186 patients undergoing emergency and elective abdominal surgery [14-16]. The NIHR Unit on Global Surgery was established in 2017 and is a consortium between the Universities of Birmingham, Edinburgh and Warwick, together with international partners. The unit's objective is to advance the education of medical students and doctors in surgical science, clinical research and audit methods by promoting participation in collaborative clinical research and audit studies.

STUDY SETTING

The study is open to any hospital worldwide that performs emergency and/or elective cholecystectomy. An eligible hospital must collect consecutive patients undergoing cholecystectomy during the specified study period, following appropriate registration of the study according to local hospital regulations.

Included centres should ensure data collection is >90% complete. Centres with >10% missing data, when including all data points, will be excluded from the final analysis and removed from the authorship.

There is no minimum number of patients per centre, as long as all eligible patients treated during the study period are included.

STUDY POPULATION

Summary

The study population includes consecutive patients, admitted to hospital within the pre-specified data collection periods, undergoing cholecystectomy as the index operation.

Inclusion Criteria

- **Age:** All adult patients (greater than or including 18 years of age).
- **Procedure:** Primary cholecystectomy, where this is the main procedure planned.
- **Approach:** Open, laparoscopic (standard and single-port), and robotic. Gasless laparoscopic and robotic approaches are included. Laparoscopic and robot converted cases are also eligible.
- **Urgency:** Elective, delayed and emergency procedures.

Exclusion Criteria

- **Procedure:** Patients having a cholecystectomy as a part of another surgical procedure; for example, Whipple's procedure, bariatric, anti-reflux, or transplant operations, should be excluded.
- **Indication:** Patients with Mirizzi syndrome should be excluded.

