- **Return to theatre:** Each patient should only be entered into the study once. Any patient returning to theatre and requiring a cholecystectomy for whatever indication, should not be included.
- **Known gallbladder malignancy:** when the diagnosis of gallbladder cancer is established pre-operatively, the patient should be excluded. However, if gallbladder cancer is found unexpectedly during or after cholecystectomy (i.e. on histology), the patient should be included.

STUDY PROCEDURES

Site Survey

In order to describe local processes and resources, each site will be asked to complete an online site survey questionnaire to delineate the variation of cholecystectomy services and training amongst included hospitals (**Appendix C**).

*Completion of the short site survey can be done by a supervising consultant (preferred) or a hospital lead trainee that is familiar with the cholecystectomy practices at your site. Completion of the site survey is necessary before the site is granted access to the online **GECKO**: Data Collection form.*

Data Collection

Collaborators will collect data on consecutive eligible patient undergoing cholecystectomy within the pre-specified data collection periods (**Table 1; page 15**). Data collectors should use a combination of the **GECKO** Case Report Form (**Appendix A**) alongside the Data Dictionary (**Appendix B**) to successfully record required data on all eligible patients. Collaborators will create clear mechanisms appropriate to their institution to identify and include all eligible patients, involving daily review of operating logbooks, multidisciplinary team meeting, admission and handover lists. Local arrangements may include daily review of the patient and notes focused on included data points.

Data will be collected and stored online via the Research Electronic Data Capture (REDCap) web application (**see pages 20-21**), hosted and managed by the University of Edinburgh, United Kingdom. No patient identifiable data will be uploaded or stored on the REDCap database.

Strategies to identify consecutive eligible patients could include:

- *Daily review of elective theatre lists.*
- *Daily review of handover sheets/emergency admission and ward lists.*
- *Daily review of theatre logbooks (both elective and emergency).*

Follow-up Period

Centres will undertake patient follow-up at two timepoints:

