The secondary endpoints include:

- Rates of achieving a critical view of safety.
- Rates of different bailout procedures initiated when safe cholecystectomy is compromised.
- 30-day and one-year rates of textbook outcomes [2] for cholecystectomy, which covers: postoperative complications (Clavien-Dindo classification), intraoperative complications (including bile duct and vascular injuries), length of stay, readmission, mortality, and postoperative imaging or intervention.
- Unsuspected gallbladder cancer rates and their 30-day and one-year outcome rates, which includes: (1) complication rates (Clavien-Dindo classification); (2) time-to-recurrence rates (time from surgery to recurrence); and (2) revisional surgery rates (liver resection, bile duct resection and/or lymph node dissection).
- A description of the global variation in the availability of cholecystectomy services, training and sustainable practice.

Control of Bias and Confounding

Data will be collected on audit standards and confounding factors for risk-adjusted analyses. These include age, sex, body mass index, American Society of Anaesthesiologists (ASA) grade, and relevant comorbidities. Variables including operative urgency, operative contamination, and operative approach will also be collected. Without appropriately adjusting for risk factors, it is likely that any findings would be biased and unable to be appropriately analysed on an international scale. A full list of required data fields is available in **Appendix B**, and on the REDCap database.

Data Analysis & Sample Size

Variation across different international health settings will be tested using the human development index (HDI) countries [17] a composite statistic of life expectancy, education and income indices published by the United Nations. Initially, data will be reported using descriptive analyses. Comparisons between groups will be undertaken using appropriate parametric and non-parametric analyses. Multilevel logistic regression multivariate models will be constructed to account for case mix, with population stratification by hospital and country as random effects.

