10. Preoperative imaging findings*	
*Only for USS / CT / MRCP, what are the findings (tick all that apply): Gallstones Thick-walled Gallbladder (≥3mm or reported as thick walled) Pericholecystic fluid CBD stones Dilated CBD. If yes: CBD diameter (record in mm, to one decimal)

11. Days between first biliary symptom onset and admission	Number of days (Whole number, day 0 is same day of first symptom onset)

12. Days between diagnosis and decision to operate	
Number of days (Whole number, day 0 is same day of diagnosis)
 
Guide for decision to operate day:
 
 For elective cases this should be the day the patient was seen in the outpatient clinic. For delayed cases this is the day the patient was LAST discharged from hospital with biliary disease. For emergency cases this should be the day the decision was made to perform an acute cholecystectomy in that emergency admission. If the patient was previously on an elective waiting list for surgery, please still use the date it was decided to perform the operation as an emergency.
13. Days between decision to operate and surgery performed	
Number of days (Whole number, day 0 is same day as surgery)

14. Urgency of surgery (Appendix D for definitions)	
Elective Delayed Emergency. If yes: Was the patient already on the elective waiting list for surgery? (Yes / No)

15. Indication for surgery (Appendix D for definitions)	
Acute calculous cholecystitis. If yes: Tokyo grade: I / II / III (Was the Tokyo grade documented in patient notes: Yes / No) Biliary colic Acalculous cholecystitis Chronic calculous cholecystitis Common Bile Duct (CBD) stone Gallbladder polyp Dyskinesia Gallstone pancreatitis. If yes: Atlanta criteria: mild / moderate / severe (Was the Atlanta criteria documented in patient notes: Yes / No)

Intra-operative Data Fields	Required data (definition / comment)
1. Mode of Anaesthesia* (Select all that apply)	
Local (subcutaneous / intraperitoneal) Regional (spine-related / regional nerve block) Sedation (e.g., midazolam) General Inhaled (sevoflurane / halothane / desflurane / Nitric Oxide (N2O) / isoflurane) Total Intravenous Volatile Anaesthetic (TIVA) *This refers to the anaesthetic used during the operation and NOT as induction agents

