6. **Living With Moderate Frailty:** People need help with all outside activities and housekeeping. Inside often have problems with stairs, need help with bathing, and may need minimal assistance with dressing.
7. **Living With Severe Frailty:** Completely dependent for cognitive and physical personal care. However, they seem stable and not at high risk of dying (within six months).
8. **Living with Very Severe Frailty:** Completely dependent for personal care and approaching end of life. Typically, they could not recover even from minor illnesses.
9. **Terminally Ill:** Approaching the end of life. This category applies to people with a life expectancy of under six months who are not otherwise living with severe frailty.

Indication for Surgery

Indication	Definition
Biliary colic	The presence of colicky right upper quadrant pain associated with gallstones or sludge on an USS, but no signs of acute cholecystitis [23]
Acute calculous cholecystitis	Clinical (right upper quadrant pain, with or without fever, WCC > 11 × 10 ⁹ /l) OR ultrasound evidence (thick walled gallbladder (≥ 3mm), OR USS tenderness over the gallbladder, the presence of gallstones) [23,24]
Acute acalculous cholecystitis	Clinical OR ultrasound evidence (thick walled gallbladder and/or pericholecystitis, USS tenderness over the gallbladder) in the absence of gallstones [23]
Chronic calculous cholecystitis	Previous clinical or ultrasound evidence (thick walled gallbladder and/or pericholecystitis, OR USS tenderness over the gallbladder OR the presence of gallstones) of cholecystitis [23]
Common bile duct stone	Common bile duct stones, as confirmed by before or at the time of surgery
Gallbladder polyp	Hyperechoic lesions on USS imaging which have no acoustic shadow and do not move with positional changes, with no overt features of malignancy [25]
Dyskinesia	Biliary like abdominal pain, occurring in a normal appearing gallbladder with a functional HIDA scan showing an abnormal gallbladder ejection fraction of less than 40% [26,27]

Tokyo Guidelines 2018 for Grading of Acute Cholecystitis

Tokyo guidelines 2018 grading [24] are listed below:

- **Grade I (mild):** No organ dysfunction and mild inflammatory changes in the gallbladder.
- **Grade II (moderate):**
 - Elevated WBC count (>18,000/mm³)
 - Palpable tender mass in the right upper abdominal quadrant
 - Duration of complaints >72 hours

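### Gallbladder cancer suspected but unproven before surgery falls between the two eligibility sentences, and no field records suspicion, so it can be counted as unsuspected

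*Protocol*

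**What the plan says.** All references are to the protocol.

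- **Exclusion Criteria, known gallbladder malignancy.** The exclusion applies "when the diagnosis of gallbladder cancer is established pre-operatively, the patient should be excluded". The next sentence adds that "if gallbladder cancer is found unexpectedly during or after cholecystectomy (i.e. on histology), the patient should be included".
- **Inclusion Criteria.** The procedure criterion is "Primary cholecystectomy, where this is the main procedure planned". Cholecystectomy done as part of another operation is excluded. The only indication that excludes a patient is Mirizzi syndrome.
- **Study Aims and Secondary Outcome Measures.** The third secondary aim is "To analyse rates and outcomes of unsuspected gallbladder cancer". The matching endpoint is "Unsuspected gallbladder cancer rates and their 30-day and one-year outcome rates", which covers complications, time to recurrence and revisional surgery. Neither place gives a working definition of unsuspected.
- **Follow-up Period.** Unsuspected gallbladder cancer is one of the two reasons given for following all patients to one year. The other is bile duct injury.
- **Appendix B, preoperative imaging findings.** The options are "Gallstones Thick-walled Gallbladder (≥3mm or reported as thick walled) Pericholecystic fluid CBD stones Dilated CBD".
- **Appendix D, Indication for Surgery.** A gallbladder polyp is a lesion "with no overt features of malignancy".

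**The concern.** Eligibility turns on whether the diagnosis was established. The endpoint turns on whether the cancer was suspected. These are different thresholds, and a patient with a suspicious lesion and no proven diagnosis lies between them.

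Two things follow. First, sites have no clear instruction, so some may enter such patients and others may leave them out. Second, once such a patient is entered and the histology is malignant, the record looks like that of a patient in whom nobody suspected cancer. The case can then be counted in the rate and also in the recurrence, complication and revisional-surgery results. A later analysis plan can define unsuspected cancer, but it cannot apply the definition to data that were never collected.

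**Working it through.** **Step 1: where a suspected but unproven cancer falls.**

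| Rule | Does it settle the case? |
|---|---|
| Exclusion: diagnosis established before surgery | No, because suspicion is not a diagnosis |
| Inclusion: cancer found unexpectedly | No, because the finding was not unexpected |
| General inclusion: primary cholecystectomy as the main planned procedure | Can be met |
| Exclusion: part of another procedure | Removes only cases planned as part of a larger operation |

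The case is not excluded, and its inclusion is left to the site.

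**Step 2: whether any collected field identifies it** (Appendices A, B and D).

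- Imaging findings: five options, none for a mass or suspicious lesion.
- Indication for surgery: eight options, none for suspected malignancy. The polyp definition rules out lesions with overt malignant features, so these have no category of their own.
- Comorbidities: solid tumour is recorded as localised or metastatic. This is neither specific to the gallbladder nor a record of suspicion.
- Histology: sent or not sent, routine or selective, benign or malignant. The reason for selective examination is not recorded.
- Nassar grade IV lists a mass, but alongside an obscured gallbladder and empyema or gangrene. It is an operative finding, recorded only for minimally invasive surgery.

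No field records pre-operative suspicion. Polyp indication, imaging used, selective histology and Nassar grade are indirect markers only.

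**Step 3: effect on the rate.** The protocol gives no gallbladder cancer rate, so there is no planned figure to reproduce. Let f be the share of counted cancers that had been suspected. With the denominator unchanged,

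counted rate / unsuspected rate = 1/(1−f).

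| f (assumed) | Factor |
|---|---|
| 10% | 1/0.90 = 1.11 |
| 25% | 1/0.75 = 1.33 |
| 50% | 1/0.50 = 2.00 |

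The factor does not depend on the underlying rate. To put it in patients, take the anticipated 15,000 (Data Analysis & Sample Size) and an assumed unsuspected rate of 0.25%, which is 37.5 cases. The count becomes 37.5/0.90 = 41.7, 37.5/0.75 = 50 or 37.5/0.50 = 75. At an assumed 0.1% (15 cases) it is 16.7, 20 or 30. At an assumed 1.0% (150 cases) it is 166.7, 200 or 300.

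**Step 4: the opposing force.** Let u be the share of truly unsuspected cancers lying in specimens that were never examined. With all operated patients as denominator,

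counted rate / true unsuspected rate = (1−u)/(1−f).

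This exceeds 1 only if f is greater than u. The documents give neither value.

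**Step 5: effect on outcomes.** If an outcome occurs in a proportion p_u of unsuspected and p_s of suspected cancers, the observed proportion is (1−f)p_u + f·p_s. The bias is f(p_s − p_u). At f = 25%, a quarter of any difference between the two groups passes into the reported result. Its sign is unknown.

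**The case against.** The strongest reply is that the inclusion sentence speaks of cancers found unexpectedly, so a site that follows it would not enter a cancer it already suspected. The exclusion of cholecystectomy within another operation removes suspected cases planned with a larger resection. The indication list has no category for suspected cancer, which suggests that such surgery was not meant to be in the cohort. These points stand as reasons why the number of such cases may be small. They do not close the gap: the sentence on unexpected findings does not exclude anyone, and a suspected case with a co-existing gallstone indication can be entered. A reader might infer that suspected cancers are definitely eligible and will be counted. The text supports only that they can be.

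A second reply is that the cases are recoverable. Sites keep the list linking patient and REDCap IDs for one-year follow-up (Follow-up Period), and the record ID is stripped only at anonymisation (Data Governance). This stands: the few malignant-histology records could be queried in time, so it would be too strong to call the cases inseparable. But the protocol plans no such query, and the window closes once the IDs are removed.

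A reader might also infer a gradient by human development index, on the ground that less work-up leaves more suspected cancers unproven. The documents do not support a direction. Less imaging could equally mean that fewer cancers are suspected at all.

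**Conclusion.** The point holds as an ambiguity in eligibility combined with a missing data item. A suspected but unproven cancer may be handled differently between sites. If entered, it can be counted as unsuspected, in the rate and in the outcomes, with no direct way to identify it.

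Taken alone, this mechanism can only raise the rate, by 1/(1−f). The factors in the working rest on assumed values of f. A reader might take them as an estimate of the inflation, but the documents give neither the cancer rate nor the number of suspected cases. The net direction is also open, because unexamined specimens lower the rate.

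The primary endpoint, compliance with audit standards, is not affected. The correction is still worth making, because the endpoint is a named secondary aim and one of the two stated grounds for one-year follow-up, and an analysis plan cannot repair it without the data.

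**What to change.** 1. In the Exclusion Criteria, state whether patients with gallbladder cancer suspected but not proven before surgery are entered.
2. Add one item to Appendices A and B: gallbladder malignancy suspected before surgery and documented in the imaging report or notes, yes or no. Requiring documentation limits differences in judgement between sites.
3. If the item cannot be collected for everyone, collect it at minimum for all malignant-histology records, through the site ID lists and before record IDs are stripped. This is enough to correct the numerator.
4. Define unsuspected gallbladder cancer as malignant histology with a no on that item. Report malignant cases with a yes separately, for the rate and for the recurrence, complication and revisional-surgery outcomes.

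The cost is one field per patient, or per malignant case under step 3, and slightly fewer events in the endpoint. Patient care does not change.
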